7.3.5 Pharmacokinetic and pharmacodynamic analyses

NA

7.4 INTERIM ANALYSES

No formal interim analysis is planned.

For BI internal decision making, preliminary exploratory analyses will be performed on an ad-hoc basis at selected time points of interest (based on the availability of pre-defined proportions of 12 weeks and 24 weeks data, respectively) before the final database lock. Each of these preliminary analyses will be based on a database snapshot. Details on the analyses will be described in the cumulative statistical analysis plan. Results of these evaluations will be distributed to the project team. No formal preliminary report will be written.

7.5 HANDLING OF MISSING DATA

Missing data will not be imputed.

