	
• Change from baseline in photoreceptor layer thickness in the junctional zone and in the perilesional zone as measured by SS-OCT at week 24 and 48• Change from baseline in the GA area as measured by FAF at week 12, 24 and 48• Change in BCVA score as assessed by ETDRS chart at a starting distance of 4 m at week 12, 24 and 48• Change in LLVA score as assessed by ETDRS chart under low luminance conditions at a starting distance of 4 m at week 12, 24 and 48• Number of scotomatous points assessed by microperimetry at week 12, 24 and 48• Change from baseline in the area of choroidal non-perfusion as measured via OCT-A at week 12, 24 and 48
Safety criteria:	Adverse events
Statistical methods:	All endpoints will be evaluated descriptively.

FLOW CHART

Trial Periods	Screening	Observation Period			
Visit	1	2 (Baseline)	3	4	5
Weeks	-4 to -1		12	24	48
Time window for visits			±2 weeks	±2 weeks	±2 weeks
Informed consent	X				
In/exclusion criteria	X	X			
Demographics	X				
Medical history	X				
BCVA testing (starting at 4 m)	X	X	X	X	X
Low Luminance Visual Acuity		X	X	X	X
SD-OCT	X	X	X	X	X
SS-OCT with OCT-A	X	X	X	X	X
FAF and Near Infrared imaging	X	X	X	X	X
Microperimetry	X ¹⁾	X	X	X	X
Concomitant medication	X	X	X	X	X
Concurrent ocular procedures	X	X	X	X	X

- 1) Microperimetry examination to be executed twice with few minutes of resting
- 2) Do be performed only after Microperimetry testing has been done in order to avoid that the microperimetry is influenced by the light used for Color Photography.
- 3) Optional

TABLE OF CONTENTS

TITLE PAGE	1
CLINICAL TRIAL PROTOCOL SYNOPSIS	2
FLOW CHART	5
TABLE OF CONTENTS	6
ABBREVIATIONS	9
1. INTRODUCTION.....	10
1.1 MEDICAL BACKGROUND.....	10
1.2 RATIONALE FOR PERFORMING THE STUDY	10
2. TRIAL OBJECTIVES AND ENDPOINTS.....	11
2.1 MAIN OBJECTIVES, PRIMARY AND SECONDARY ENDPOINTS.....	11
2.1.1 Main objectives.....	11
2.1.2 Primary endpoints.....	11
2.1.3 Secondary endpoints	11
2.2 FURTHER OBJECTIVES AND FURTHER ENDPOINTS	11
2.2.1 Further objectives	11
2.2.2 Further endpoints	12
3. DESCRIPTION OF DESIGN AND TRIAL POPULATION.....	13
3.1 OVERALL STUDY DESIGN AND PLAN	13
3.2 SELECTION OF STUDY POPULATION.....	13
3.2.1 Main diagnosis for study entry	13
3.2.2 Inclusion criteria	13
3.2.3 Exclusion criteria	14
3.2.4 Withdrawal of patients from study participation	15
3.2.4.1 Withdrawal of consent for study participation.....	15
3.2.4.2 Discontinuation of the study by the sponsor	15
4. TREATMENTS.....	16

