2.1.2 Primary endpoints

All of the following endpoints will be assessed for the study eye.

- Change from baseline in retinal sensitivity in the junctional zone and in the perilesional zone of the largest atrophic loci as assessed by microperimetry for the evaluation of macular functional response at week 12
- Change from baseline in RPE layer thickness in the junctional zone and in the perilesional zone as measured by SS-OCT at week 12
- Change from baseline in photoreceptor layer thickness in the junctional zone and in the perilesional zone as measured by SS-OCT at week 12

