2.1.3 Secondary endpoints

[figure not shown]
All of the following endpoints will be assessed for the study eye.

- Change from baseline in retinal sensitivity in the junctional zone and in the perilesional zone of the largest atrophic loci as assessed by microperimetry at week 24 and 48
- Change from baseline in RPE layer thickness in the junctional zone and in the perilesional zone as measured by SS-OCT at week 24 and 48
- Change from baseline in photoreceptor layer thickness in the junctional zone and in the perilesional zone as measured by SS-OCT at week 24 and 48
- Change from baseline in the GA area as measured by Fundus Autofluorescence (FAF) at week 12, 24 and 48
- Change in Best Corrected Visual Acuity (BCVA) score as assessed by Early Treatment Diabetic Retinopathy Scale (ETDRS) chart at a starting distance of 4 m at week 12, 24 and 48
- Change in Low Luminance Visual Acuity (LLVA) score as assessed by ETDRS chart under low luminance conditions at a starting distance of 4 m at week 12, 24 and 48
- Number of scotomatous points assessed by microperimetry at week 12, 24 and 48
- Change from baseline in the area of choroidal non-perfusion as measured via Optical Coherence Tomography Angiography (OCT-A) at week 12, 24 and 48

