7. STATISTICAL METHODS AND DETERMINATION OF SAMPLE SIZE

7.1 STATISTICAL DESIGN - MODEL

The main objective of this longitudinal observational study is to investigate the use of microperimetry and SS-OCT in assessing the natural changes of retinal sensitivity and anatomy in patients with GA. In addition, changes in several other ophthalmologic measurements over time will be examined.

To this end, point estimates and confidence intervals (CIs) for the primary and secondary endpoints will be determined. Correlations between interesting pairs of outcome measures will be assessed.

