7.3 PLANNED ANALYSES

All subjects entering the study will be included in the analyses. Protocol violations will be defined in TSAP. A per-protocol set will be defined accordingly thereafter.

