7.3.1 Primary endpoint analyses

For each primary endpoint (see [section 2.1.2](#)), baseline is defined as the measurement obtained at Visit 2.

The following descriptive statistics will be calculated for the measurements related to the primary endpoints at each time point, as well as for the changes from baseline: N, arithmetic mean, Standard Deviation (SD), minimum, median, maximum, percentiles, arithmetic coefficient of variation.

Correlations (both Pearson and rank-based) of the changes from baseline of retinal sensitivity in the junctional zone and in the perilesional zone, respectively, of the largest atrophic loci as measured by microperimetry to the following endpoints will be estimated:

- Change from baseline in RPE layer thickness in the junctional zone and in the perilesional zone, respectively, as measured by SS-OCT and by SD-OCT
- Change from baseline in photoreceptor layer thickness in the junctional zone and in the perilesional zone, respectively, as measured by SS-OCT and by SD-OCT
- Changes from baseline in GA area as measured by FAF
- Change from baseline in the area of choriocapillaris flow deficits as measured via OCT-A at week 12, 24 and 48

Individual data as well as summary statistics will be visualised in respective graphical presentations, e.g. scatter plots or box-plots.

Correlations between the primary endpoints and continuous baseline characteristics will be investigated if necessary.

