7.7 DETERMINATION OF SAMPLE SIZE

The chosen number of 50 patients with GA is assumed to be sufficient for the purpose of investigating the distribution of the microperimetry measurements and their short-term changes in this patient population.

In particular, for this trial a precision (the half-width of the 95% CI) of 0.3 dB for the mean change from baseline in retinal sensitivity has been considered sufficient by the project team. [Table 7.5: 1](#) provides an overview of numbers needed for obtaining a 95% CI for the mean change from baseline in retinal sensitivity with a given half width with at least 90% probability, under various assumptions for the underlying SD. For example, assuming an SD of 0.9, the trial will need 47 patients in order to achieve two-sided 95% CIs for the given precision with a probability of 90%. For an SD of 0.7, the required sample size would be 31. Note that the SD for longitudinal changes from baseline of the retinal sensitivity in 8 patients with GA as seen in Wu et al. [[R17-1097](#)] was about 0.62.

Table 7.5: 1 Number of patients needed for obtaining a 95% CI for the mean change from baseline of retinal sensitivity with a given half width with at least 90% probability, for different SD values

Half-width of CI [dB]	Assumed SD			
	0.60	0.7	0.8	0.9
0.20	47	61	77	96
0.25	33	42	53	64
0.30	24	31	39	47

The calculation was performed as described by Julious [[R11-5230](#), Chapter 8] using R Version 3.3.2.

8. INFORMED CONSENT, TRIAL RECORDS, DATA PROTECTION, PUBLICATION POLICY, AND ADMINISTRATIVE STRUCTURE

The study will be carried out in compliance with the protocol and the ethical principles laid down in the Declaration of Helsinki.

Standard medical care (prophylactic, diagnostic and therapeutic procedures) remains the responsibility of the treating physician of the patient.

The BI transparency and publication policy can be found on the following web page: trials.boehringer-ingelheim.com. The rights of the investigator and of the sponsor with regard to publication of the results of this trial are described in the investigator contract. As a rule, no trial results should be published prior to finalization of the Clinical Trial Report (CTR). The certificate of insurance cover is made available to the investigator and the patients, and is stored in the Investigator Site File (ISF).

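### Week-24 and week-48 changes are summarised only from patients measured at that visit; a repeated-measures model would reduce the bias if faster progressors leave, and remove it only if data are missing at random

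*Combined protocol and SAP*

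**What the plan says.** Section 7.1 is headed as the statistical model but names none. It promises that "point estimates and confidence intervals (CIs) for the primary and secondary endpoints will be determined". Section 7.3.1 gives the method for the primary endpoints: "The following descriptive statistics will be calculated for the measurements related to the primary endpoints at each time point", and likewise for the changes. Section 7.3.2 says the secondary endpoints are analysed descriptively, and the synopsis says the same of everything: "All endpoints will be evaluated descriptively". Section 7.5 consists of one statement: "Missing data will not be imputed".

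The primary endpoints are at week 12 (section 2.1.2), for example "Change from baseline in RPE layer thickness in the junctional zone and in the perilesional zone as measured by SS-OCT at week 12". The same measures at weeks 24 and 48 are secondary (section 2.1.3).

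Section 7.3 adds that "All subjects entering the study will be included in the analyses". That defines the analysis set. It supplies no value for a missed visit, so a patient without a week-48 measurement adds nothing to the week-48 mean.

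The documents state no expected dropout, no missing-data assumption, no longitudinal model and no sensitivity analysis for missing data. Section 7.3 refers to a TSAP and section 7.4 to a cumulative statistical analysis plan; no such text is among the documents reviewed.

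**The concern.** The study follows a progressive disease for 48 weeks in patients aged 60 or over who must be able to perform microperimetry. Several provisions make loss related to progression plausible:

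- Patients should not be in an interventional trial for this condition while in the study (section 4.2.2.1), and worsening could prompt a patient to choose one.
- The length of observation depends on whether treatments are approved (section 3.1).
- Nothing more is collected after consent is withdrawn (section 3.2.4.1).

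If those who decline faster leave, each later mean describes a progressively slower-declining subset of the starting group. The interval around that mean shows no sign of the shift. Estimation is the purpose here: section 1.2 says early-trial decisions may rest on such changes, and section 7.4 foresees internal use of the results. The cost would be natural-history estimates that are too small. No error rate is at stake, because nothing is tested confirmatively (section 7.2).

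**Working it through.** **1. The plan's own figure.** Section 7.7 requires a 95% CI half-width w = 0.3 dB with 90% probability at SD 0.9 dB. The condition is n ≥ t²(0.975, n−1) × SD²/w² × χ²(0.90, n−1)/(n−1).

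- n = 47: 2.0129² × 0.81/0.09 × 58.64/46 = 46.5 ≤ 47, met.
- n = 46: 2.0141² × 0.81/0.09 × 57.51/45 = 46.7 > 46, not met.

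So n = 47, as stated. All 12 cells of Table 7.5: 1 reproduce. The calculation makes no separate allowance for missing values, and it concerns width, not bias.

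**2. Inputs for the bias check.** From the documents: change at weeks 12, 24 and 48; SD 0.9 dB; half-width 0.3 dB. Assumed, because the documents are silent: the same SD at each visit; correlation 0.4 or 0.7 between visits; 20% cumulative dropout over three intervals, so 1 − 0.8^(1/3) = 7.2% per interval; logistic dropout with slope 1.5 per SD of worse change.

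**3. Estimators**, each on 400,000 simulated patients so that sampling error is negligible:

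- Available-case: the mean of the change among patients observed at that visit.
- Repeated-measures likelihood under monotone dropout, without a baseline covariate: m12 = the week-12 mean; m24 = a + b·m12, from the regression of week 24 on week 12 in those observed at week 24; m48 = c + d·m12 + e·m24, from the regression of week 48 on both earlier visits.

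**4. Results.** Bias in dB; positive means decline is understated; ranges run over the two correlations.

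| Dropout depends on | Visit | Available-case | Repeated-measures |
|---|---|---|---|
| Nothing (completely at random) | all | 0.00 | 0.00 |
| Last observed change | week 12 | 0.00 | 0.00 |
| | week 24 | +0.03 to +0.06 | 0.00 |
| | week 48 | +0.06 to +0.10 | 0.00 |
| Current, unseen change | week 12 | +0.08 | +0.08 |
| | week 24 | +0.11 to +0.13 | +0.10 |
| | week 48 | +0.13 to +0.17 | +0.11 |

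With 10% to 30% dropout related to the last observed change, the week-48 available-case bias runs from +0.03 to +0.15.

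**5. Variant.** With all of the 20% loss placed after week 12 and driven by the last observed change, the week-48 available-case bias is about 0.09 to 0.16 dB and the model's about 0.00. When loss depends on the unseen current change, the model still leaves about 0.08 to 0.12 dB of 0.16 to 0.19 dB.

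**6. Scale.** Combining steps 4 and 5 for dropout related to the last observed change gives 0.06 to 0.16 dB. Against the target half-width this is 0.06/0.3 = 20% to 0.16/0.3 = 53%. The bias is proportional to the SD. At the 0.62 dB that section 7.7 cites from 8 patients, it would be 0.06 × 0.62/0.9 = 0.04 to 0.16 × 0.62/0.9 = 0.11 dB.

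**The case against.** The strongest reply is that the study is exploratory, its primary endpoints fall at the first post-baseline visit, and no section says that faster progressors drop out. Entry requires ability and willingness to attend all visits and visual acuity of 20/63 or better. Ocular conditions likely to need intervention or to cost vision are excluded. Follow-up cut short by an approval need not depend on progression. Section 7.3.1 lists no confidence interval, so how those promised in section 7.1 would be computed is inferred from the per-visit plan, and a TSAP could add a model. All of this stands. It makes the concern conditional and confines it mainly to secondary results, but it does not give the plan a method that copes with selective loss.

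Four stronger readings are tempting, and the documents do not support them:

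- *A repeated-measures model uses the same data without bias.* That holds only under missing at random with a correctly specified model. Patients who become untestable may be lost because of function nobody recorded. In that case the model removed only about 10% to 40% of the bias at weeks 24 and 48 (step 4), and none at week 12.
- *The no-imputation rule is the fault.* A repeated-measures model imputes nothing either. The gap is per-visit summaries with no longitudinal model.
- *The primary results are compromised.* A patient lost before week 12 has no post-baseline value, so the model helps there only as far as baseline predicts change.
- *Decline is understated by a large, known percentage.* The documents give neither a mean week-48 change nor a dropout rate. Percentages of 10% to 22% arise only by assuming a mean change of −1.5 dB, 20% to 29% missing, and a spread above the SDs in section 7.7. Those SDs do concern short-term change, so the week-48 SD could be larger, but no figure is given.

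**Conclusion.** The point holds, conditionally and for weeks 24 and 48. Followed as written, the plan estimates later change from that visit's attendees, and decline is understated if faster progressors leave. Under the stated assumptions, with dropout related to the last observed change, the week-48 shift is roughly 0.06 to 0.16 dB, a fifth to about half of the half-width that the sponsor judged sufficient. A repeated-measures model is about unbiased there. Under loss that depends on unseen progression it helps only in part; under completely random loss the two methods agree.

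The dropout rate, correlations and dropout slope are assumptions, so the figures illustrate and do not predict. They apply to retinal sensitivity only, since the documents give no SD for layer thickness or lesion area. The change is worth making because it is cheap and the study exists to estimate these changes.

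**What to change.** Keep every descriptive table and the no-imputation rule, and add the following to section 7.3 or the TSAP:

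- For the continuous change endpoints, by zone where applicable, take the section 7.1 point estimates and 95% CIs at weeks 12, 24 and 48 from a mixed model for repeated measures: visit as a factor, baseline as a covariate centred at the mean of all patients entered, unstructured within-patient covariance, REML. Report them beside the available-case means.
- State that the model is valid under missing at random.
- Tabulate the timing of and reasons for dropout and for unmeasurable visits.
- Add a delta-adjusted sensitivity analysis at weeks 24 and 48. In its simplest form it needs no imputation: the visit mean moves by the proportion missing times delta. At 20% missing, a delta of 0.5 dB moves the mean by 0.20 × 0.5 = 0.10 dB.
- Leave the number of scotomatous points descriptive, or use a count model; a Gaussian model of change does not suit it.

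The cost is TSAP wording and modest programming. The model relies on missing at random, but that is a weaker assumption than the available-case means need. It does not alter the planned correlations, which would still use patients with both measurements.

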7.6 RANDOMISATION

NA

7.7 DETERMINATION OF SAMPLE SIZE

The chosen number of 50 patients with GA is assumed to be sufficient for the purpose of investigating the distribution of the microperimetry measurements and their short-term changes in this patient population.

In particular, for this trial a precision (the half-width of the 95% CI) of 0.3 dB for the mean change from baseline in retinal sensitivity has been considered sufficient by the project team. [Table 7.5: 1](#) provides an overview of numbers needed for obtaining a 95% CI for the mean change from baseline in retinal sensitivity with a given half width with at least 90% probability, under various assumptions for the underlying SD. For example, assuming an SD of 0.9, the trial will need 47 patients in order to achieve two-sided 95% CIs for the given precision with a probability of 90%. For an SD of 0.7, the required sample size would be 31. Note that the SD for longitudinal changes from baseline of the retinal sensitivity in 8 patients with GA as seen in Wu et al. [[R17-1097](#)] was about 0.62.

Table 7.5: 1 Number of patients needed for obtaining a 95% CI for the mean change from baseline of retinal sensitivity with a given half width with at least 90% probability, for different SD values

Half-width of CI [dB]	Assumed SD			
	0.60	0.7	0.8	0.9
0.20	47	61	77	96
0.25	33	42	53	64
0.30	24	31	39	47

The calculation was performed as described by Julious [[R11-5230](#), Chapter 8] using R Version 3.3.2.

8. INFORMED CONSENT, TRIAL RECORDS, DATA PROTECTION, PUBLICATION POLICY, AND ADMINISTRATIVE STRUCTURE

The study will be carried out in compliance with the protocol and the ethical principles laid down in the Declaration of Helsinki.

Standard medical care (prophylactic, diagnostic and therapeutic procedures) remains the responsibility of the treating physician of the patient.

The BI transparency and publication policy can be found on the following web page: trials.boehringer-ingelheim.com. The rights of the investigator and of the sponsor with regard to publication of the results of this trial are described in the investigator contract. As a rule, no trial results should be published prior to finalization of the Clinical Trial Report (CTR). The certificate of insurance cover is made available to the investigator and the patients, and is stored in the Investigator Site File (ISF).

8.1 TRIAL APPROVAL, PATIENT INFORMATION, INFORMED CONSENT

This study will be initiated only after all required legal documentation has been reviewed and approved by the respective Institutional Review Board (IRB) / Independent Ethics Committee (IEC) according to national and international regulations. The same applies for the implementation of changes introduced by amendments.

Prior to patient participation in the trial, written informed consent must be obtained from each patient (or the patient's legally accepted representative) according to regulatory and legal requirements of the participating country. Each signature must be personally dated by each signatory and the informed consent and any additional patient-information form retained by the investigator as part of the trial records. A signed copy of the informed consent and any additional patient information must be given to each patient or the patient's legally accepted representative."

The investigator must give a full explanation to study patients based on the patient information form. A language understandable to the patient should be chosen, technical terms and expressions avoided, if possible.

The patient must be given sufficient time to consider participation in the study. The investigator obtains written consent of the patient's own free will with the informed consent form after confirming that the patient understands the contents. The investigator must sign (or place a seal on) and date the informed consent form. If a trial collaborator has given a supplementary explanation, the trial collaborator also signs (or places a seal on) and dates the informed consent.

Re-consenting may become necessary when new relevant information becomes available and should be conducted according to the sponsor's instructions.

The consent and re-consenting process should be properly documented in the source documentation.

8.2 DATA QUALITY ASSURANCE

A quality assurance audit/inspection of this trial may be conducted by the sponsor, sponsor's designees, or by IRB / IEC or by regulatory authorities. The quality assurance auditor will have access to all medical records, the investigator's trial-related files and correspondence, and the informed consent documentation of this clinical trial.

